8. GENERAL CONSIDERATIONS FOR DATA ANALYSES AND HANDLING

Data will be listed and summarized according to GlaxoSmithKline reporting standards, where applicable.

PWH115760

8.1. Reporting Conventions

- All the data will be listed for clinical safety and tolerability evaluation.
- Missing data will not be imputed.
- Actual times relative to study drug dosing will be used in data listings. Planned times relative to study drug dosing will be used in data summaries.
- Any changes from the analyses within this reporting and analysis plan will be stated in the final study report
- Analyses are performed using the SAS/STAT® module of the SAS® System, Version 9.3 (SAS and SAS/STAT are registered trademarks of the SAS Institute Inc., Cary, NC, USA). Programs will be imported into HARP and the final output will be produced by running drivers in HARP.
- Sections 10 to 13 contain the details regarding the planned analyses and see Section 15.2 for the data displays for decision critical results.
- For subjects who entered multiple cohorts, the subject number of the very first entry will be used as the subject ID for reporting purpose.

PWH115760

8.2. Data Management

The data collection tool for this study will be GSK-defined electronic case report forms (CRFs). In all cases, subject initials will not be collected nor transmitted to GSK. Subject data necessary for analysis and reporting will be entered/transmitted into a validated database or data system. Clinical data management will be performed in accordance with applicable GSK standards and data cleaning procedures. Original CRFs will be retained by GSK, while the investigator will retain a copy.

Data Type	Source	Format of Data	Planned Date of Final File ¹	Responsibility
Study population, Safety, PD sampling	Inform Database	IDSL data	DBR	CPSSO
Safety Laboratory Data	Quest Central Laboratory	IDSL data	DBR	CPSSO/External Vendor
PK Concentration	SMS2000 data files	data file	DBR	DMPK
Biomarker/bio burden	External Vendor Forsyth files through external alliance portal	.xlsx and. cel files	DBR	CPSSO/External Vendor/Target Sciences
PD	CRO CPC – files through external alliance portal	IDSL data	DBR	CPSSO/External Vendor

¹This is for study teams to determine upfront if there is a possibility of not meeting the completion of the CPSR within 6 months of LSLV (i.e. novel data that may not be available until several months after LSLV).

8.3. Premature Withdrawal and Missing Data

All subjects who withdraw prematurely from the study/study drug will be documented and the reason for their withdrawal recorded in the final Clinical Pharmacology Study Report (CPSR). All available data from subjects who withdraw will be listed and all available planned data will be included in the summaries according to the populations defined in Section 5.

In the event that the study is prematurely discontinued, all available data will be listed and a review carried out by the study team to assess which statistical analyses are still considered appropriate.

No imputations will be made for missing data.

8.4. Protocol Deviations

Important protocol deviations (including deviations related to study inclusion/exclusion criteria, conduct of the trial, patient management or patient assessment) will be listed.

Protocol deviations will be tracked by the study team throughout the conduct of the study in accordance with. Data will be reviewed prior to unblinding and freezing the database to ensure all important deviations are captured and categorized on the protocol deviations dataset. This dataset will be the basis for listings of protocol deviations.

A separate listing of all inclusion/exclusion deviations will also be provided. This listing will be based on data as recorded on the inclusion/exclusion page of the eCRF.

8.5. Baseline Definition

Baseline values for safety and PD parameters will be calculated for each subject as defined in the following table:

The following table indicates the baseline observations to be used in the analyses:

Parameter	Visit of Baseline Observation
Safety:	
ECG	Day 1 pre-dose
Laboratory	Day 1 pre-dose
Vital Signs	Day1 pre-dose (weight/height at screening)
Demographics	Screening
PD:	
Gene expression	Day 1 pre-dose
Biomarkers	Day 1 pre-dose
Physical characteristics	Day 1 pre-dose
Clinical characteristics	Day 1 pre-dose
PK parameters	Day 1

Note for cohort 2, baseline should be Day1 predose on Period 2.

For those without baseline run in, screening visit should come from baseline run in for reporting purpose.

PWH115760

If, for any parameter, the baseline has a missing value or below LLQ, then the most-recent non-missing value obtained before dosing will be used as the baseline value for that parameter.

8.6. Derived and Transformed Data

8.6.1. Change from Baseline

The change from baseline will be calculated for each post-baseline time-point by subtracting the baseline values from the individual post-baseline values. If either the baseline or post-baseline value is missing, the change from baseline will be set to missing as well.

8.6.2. Multiple Measurements at One Time-point

Where planned multiple measurements are recorded for a particular time point, the mean of the measurements will be calculated and used in any derivation of summary statistics. However all available data will be listed.

8.6.3. Derived parameters for EPO

Cmax, tmax and AUC of EPO concentration will be derived for each subject by the study day (Part A: Day 1; Part B: Day 1, Day 8, Day14 or Day21).

The maximum observed concentration (Cmax) and the first time of its occurrence (tmax) will be obtained directly from the EPO concentration-time data for each subject by study day.

AUC will be calculated using linear trapezoidal rules. Let C1 and C2 be two adjacent concentration point and T1 and T2 be corresponding two adjacent time points, then according to the trapezoidal rule, the partial AUC between T1 and T2, $AUC[T1, T2] = (C1+C2)*(T2-T1)/2$, and total AUC is the sum of all partial AUC's within the defined time window.

8.6.4. Derived parameters for time to event measures

Time to events for wound healing will be derived using a first occurrence approach as follows:

x% healed: the x% healing event is recorded when percent change from baseline of area of wound (or volume of wound) is -x% or lower; the time of first occurrence is the event time, x can be 30, 50 or 75;

The full closure event is recorded when the wound is fully healed, the event time is the first occurrence time of the event.

PWH115760

The event time (number of days) = date of event occurrence – date of Randomization +1

8.6.5. Derived Parameters for Metabolite:Plasma Exposure Ratios

If data permit, Metabolite : Parent drug systemic exposure ratios (corrected for molecular weight) will be calculated for plasma AUC and Cmax parameters as follows:

$$\text{M: P AUC ratio} = \frac{\text{Metabolite AUC}/\text{Metabolite MW}}{\text{GSK1278863 AUC}/\text{GSK1278863 MW}}$$

$$\text{M: P Cmax ratio} = \frac{\text{Metabolite Cmax}/\text{Metabolite MW}}{\text{GSK1278863 Cmax}/\text{GSK1278863 MW}}$$

Compound	Molecular Weight (MW)
GSK1278863 (parent)	393.442
GSK2391220 (metabolite)	425.442
GSK2531403 (metabolite)	425.442
GSK2487818 (metabolite)	425.442
GSK2506102 (metabolite)	425.442
GSK2531398 (metabolite)	425.442
GSK2531401 (metabolite)	441.442

PWH115760

8.6.6. Derived Parameters for Actual Drug Administered

In Part A, the difference of syringe weights will be calculated for determination of amount of dose administered. Predose syringe weight will reflect the empty syringe weight plus amount of drug to be administered; postdose syringe weight will reflect the empty syringe weight plus any residual drug remaining in syringe after dosing.

Amount of Dose Administered

$$= \text{Syringe weight predose} - \text{Syringe weight postdose}$$

In Part B, the difference in ointment tube weights will be calculated for a general assessment of patient compliance by determining the average amount of dose administered in the repeat dose portion of the study. Predose tube weight will reflect the tube weight prior to dosing; postdose tube weight will reflect the tube weight when the patient returns for their office visits throughout the repeat dose portion of the study.

Average Amount of Dose Administered

$$= \frac{\text{Tube weight predose} - \text{Tube weight postdose}}{\text{Number of days}}$$

8.7. Values of Potential Clinical Importance

Laboratory Values of Potential Clinical Importance (Healthy Volunteers)

Hematology Analyte	Effect	Relative – Low (Multipliers of LLN)	Relative – High (Multipliers of ULN)
White Blood Cell Count ($\times 10^9/\text{L}$)		0.5	2
Neutrophil Count ($\times 10^9/\text{L}$)		0.75	
Hemoglobin (g/L)	Low	< -25 decrease from baseline	
	Male		1.1
	Female		1.1
Hematocrit (Ratio of 1)	Low	< -0.1 decrease from baseline	
	Male		1.1
	Female		1.1
Platelet Count ($\times 10^9/\text{L}$)		0.5	1.75
Lymphocytes ($\times 10^9/\text{L}$)		0.75	

CONFIDENTIAL

CM2009/00071/00

PWH115760

Chemistry Analyte	Effect	Relative – Low (Multipliers of LLN)	Relative – High (Multipliers of ULN)
Albumin (g/L)			
Calcium (mmol/L)		0.85	1.1
Creatinine (μmol/L)	High	≥ 22 increase from baseline (Note 22 μmol/L ≈ 0.25 mg/dL)	
Glucose (mmol/L)		0.71	1.41
Potassium (mmol/L)		0.86	1.1

Liver Function Test Analyte	Effect	Potential Clinical Importance (PCI) Range	Unit
ALT/SGPT	High	≥ 2x ULN	U/L
AST/SGOT	High	≥ 2x ULN	U/L
AlkPhos	High	≥ 2x ULN	U/L
T Bilirubin	High	≥ 1.5xULN	μmol/L
T. Bilirubin + ALT	High	≥ 1.5xULN T. Bilirubin + ≥ 2x ULN ALT	μmol/L U/L

ECG Values of Potential Clinical Importance (Healthy Volunteers)

ECG Parameter	Potential Clinical Importance Range (PCI)	Unit
Absolute QTc interval	>450	msec
Increase from baseline QTc	>60	msec
QRS interval	>110	msec

Vital Sign Values of Potential Clinical Importance (Healthy Volunteers)

Vital Sign Parameter	Potential Clinical Importance Range (PCI)	Unit
Systolic Blood Pressure	< 85 or > 160	mmHg
Diastolic Blood Pressure	< 45 or > 100	mmHg
Heart Rate	< 40 or > 110	bpm

PCI for patients

CONFIDENTIAL

CM2009/00071/00

PWH115760

Hematology Analyte	Effect	Relative – Low (Multipliers of LLN)	Relative – High (Multipliers of ULN)
White Blood Cell Count (x10 ⁹ / L)		0.5	2
Neutrophil Count (x10 ⁹ / L)		0.75	
Hemoglobin (g/L)	Low	< -25 decrease from baseline	
	Male		1.1
	Female		1.1
Hematocrit (Ratio of 1)	Low	< -0.1 decrease from baseline	
	Male		1.1
	Female		1.1
Platelet Count (x10 ⁹ / L)		0.5	1.75
Lymphocytes (x10 ⁹ / L)		0.75	

Chemistry Analyte	Effect	Relative – Low (Multipliers of LLN)	Relative – High (Multipliers of ULN)
Calcium (mmol/L)		0.85	1.1
Creatinine (μmol/L)	High	≥ 22 increase from baseline (Note 22 μmol/L ≈ 0.25 mg/dL)	
Glucose (mmol/L)		0.5	2
Potassium (mmol/L)		.75	1.25
Sodium (mmol/L)		.9	1.1

Liver Function Test Analyte	Effect	Potential Clinical Importance (PCI) Range	Unit
ALT/SGPT	High	≥ 2x ULN	U/L
AST/SGOT	High	≥ 2x ULN	U/L
AlkPhos	High	≥ 2x ULN	U/L
T Bilirubin	High	≥ 1.5xULN	μmol/L
T. Bilirubin + ALT	High	≥ 1.5xULN T. Bilirubin + ≥ 2x ULN ALT	μmol/L U/L

PWH115760

ECG Values of Potential Clinical Importance (DFU Patients)

ECG Parameter	Potential Clinical Importance Range (PCI)	Unit
Absolute QTc interval	>500 for patients with baseline bundle branch block (BBB) and >450 for patient without a baseline BBB	msec
Increase from baseline QTc	>60	msec
QRS interval	>110	msec

Vital Sign Values of Potential Clinical Importance (DFU Patients)

Vital Sign Parameter	Potential Clinical Importance Range (PCI)	Unit
Systolic Blood Pressure	< 85 or > 160	mmHg
Diastolic Blood Pressure	< 45 or > 100	mmHg
Heart Rate	< 40 or > 110	bpm

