The decision to proceed to the next dose level of GSK1278863 will be made by the GSK Study Team and the Investigator based on safety (including plasma hemoglobin (Hb) levels), tolerability and preliminary pharmacokinetic and/or pharmacodynamic data obtained in at least 4 subjects for single dosing (SD) (Part A) and 12 subjects for repeat dosing (RD) (Part B) at the prior dose level. The actual doses to be administered may be adjusted based on safety, tolerability and preliminary pharmacokinetic and/or pharmacodynamic data at previous dose levels; these dose adjustments may involve either an increase or a decrease in the planned dose. Pharmacokinetic data will be evaluated as appropriate throughout the study to continue dose escalation, or to adjust or discontinue dose escalation as necessary. The chosen doses will be appropriate to prevent the projected Cmax and AUC(0-t) from exceeding 1400ng/mL and 14,800ng.h/mL, respectively (NOAEL exposures from the three-month monkey safety assessment study). Notably, the systemic activity of the compound has robust effects on erythropoiesis. Therefore, doses will be selected to minimize systemic exposure of the compound to limit elevations in hemoglobin. Hence, the exposures will be held to a much lower than NOAEL threshold by selecting maximal dose levels which are predicted to limit systemic exposure at or below levels equivalent to a 15mg oral dose (Cmax 286ng/mL; AUC 650ng.h/mL). (Note: modeling efforts predict that average exposures of the currently targeted highest dose (3mg of the 1% formulation; Cmax 55.3ng/mL; AUC 334ng.h/mL) will be at or below the 10mg oral dose exposures (Cmax 135ng/mL; AUC 319ng.h/mL). The 15mg oral dose has been demonstrated to maintain average rates of hemoglobin elevation to <1g/dL over a 2 week period.

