4.5.1.1. Hemoglobin Stopping Criteria

A patient that experiences an absolute increase in hemoglobin of 1.5g/dL above their baseline level at any time will be withdrawn from the study.

Should hemoglobin values achieve the above set criteria, additional samples may be collected every 2-3 days and appropriate procedures (venesection or erythrocytapheresis) may be considered and implemented at the discretion of the investigator until the laboratory result returns to the patient's normal range.

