14.1.2. Safety Figures & Tables

Tables

Table No.	Population	IDSL No. / Example Shell	Title	Programming Notes	Deliverable Priority
10.xx	All Subjects	Ex1	Summary of Exposure data for Part A		SAC, in stream
10.xx	All Subjects	Ex1	Summary of Exposure data for Part B		SAC, in stream
10.xx	All Subjects	AE1	Summary of All Adverse Events		SAC, in stream
10.xx	All Subjects	AE1	Summary of Drug Related Adverse Events		SAC, in stream
10.xx	All Subjects	AE1	Summary of AEs Leading to Withdrawal		SAC, in stream
10.xx	All Subjects	AE5	Summary of Adverse Events by Maximum Intensity		SAC, in stream
10.xx	All Subjects	LB1	Summary of Chemistry Data		SAC
10.xx	All Subjects	LB1	Summary of Hematology Data		SAC
10.xx	All Subjects	VS1	Summary of Vital Signs		SAC, in stream
10.xx	All Subjects	EG2	Summary of ECG Values		SAC, in stream
10.xx	All Subjects	LB2	Summary of Hematology Data Outside the Reference Range		SAC
10.xx	All Subjects	LB2	Summary of Chemistry Data Outside the Reference Range		SAC
10.xx	All Subjects	VS2	Summary of Vital Sign Data Outside Clinical Concern Range		SAC
10.xx	All Subjects	EG2	Summary of Change from baseline ECG Values		SAC, in stream
10.xx	All Subjects	EG1	Summary of ECG Findings		SAC, in stream
10.xx	All Subjects	Exhibit F	Summary of raw EPO data by treatment		SAC, in stream
10.xx	All Subjects	AE15	Summary of Common Non-Serious Adverse Events by System Organ Class and Preferred Term	AE is considered common if more than one subject experiences it regardless of treatment	SAC
10.xx	All Subjects	AE16	Summary of Serious Events by System Organ Class and Preferred Term (Number of Subjects and Occurrences)		SAC

Figures

Figure No.	Population	IDSL No. / Example Shell	Title	Programming Notes	Deliverable Priority
10.xx	All Subjects	Exhibit E	The Time course of EPO values of treatment period		SAC, in stream

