14.1.5. ICH Listings

Table No.	Population	IDSL No. / Example Shell	Title	Programming Notes	Deliverable Priority
1	All Subjects	DM4	Listing of Demographic Characteristics		SAC, in stream
2	All Subjects		Listing of all Clinical Chemistry Laboratory Data for Subjects with Abnormalities of Potential Clinical Importance		SAC
3	All Subjects	IE3	Listing of Subjects with Inclusion/exclusion Criteria Deviations		SAC
4	All Subjects	DM10	Listing of Race		SAC
5	All Subjects	CM3	Listing of Concomitant Medications by Generic Term		SAC
6	All Subjects	ES3	Listing of Reason for Withdrawal		SAC, in stream
7	All Subjects	DV1A	Listing of Subjects with study protocol Deviations		SAC
8	All Subjects	EX3	Listing of Exposure Data		SAC
9	All Subjects	AE7	Listing of Subject Numbers for Individual Adverse Events		SAC
10	All Subjects	AE8	Listing of all Adverse Events		SAC
11	All Subjects	AE9a	Listing of AEs with No Resolution Date		SAC
12	All Subjects	LB5	Listing of Clinical Chemistry of Potential Clinical Importance		SAC
13	All Subjects	LB12	Listing of all Clinical Hematology Laboratory Data for Subjects with Abnormalities of Potential Clinical Importance		SAC
14	All Subjects	CP_VS4	Listing of All Vital Signs for Subjects with Values of Potential Clinical Importance		SAC

Table No.	Population	IDSL No. / Example Shell	Title	Programming Notes	Deliverable Priority
15	All Subjects	CP_VS4	Listing of Vital Signs of Potential Clinical Importance		SAC
16	All Subjects	CP_EG6a	Listing of All ECG Values for Subjects with a Value of Potential Clinical Importance		SAC
17	All Subjects	CP_EG3	Listing of ECG Values of Potential Clinical Importance		SAC
18	All Subjects	CP_EG5	Listing of Abnormal ECG Findings		SAC
19	All Subjects	IE4 (XO)	Listing of Subjects with Inclusion/Exclusion Criteria Deviations		SAC
20	Enrolled	ES7	Listing of Reasons for Run-In Failure		SAC
21	All Subjects	Exhibit Q	Listing of prior Medications		SAC
22	All Subjects	AE8	Listing of Serious Adverse Events		SAC, in stream

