14.1.6. Other Listings

Table No.	Population	IDSL No. / Example Shell	Title	Programming Notes	Deliverable Priority
1	PD	Exhibit N	Listing PD Endpoints by Treatment and Time Points for Part A and Part B Respectively - Skin Perfusion Pressure and Pulse Volume Recording		SAC
2	PD	Exhibit N	Listing PD Endpoints by Treatment and Time Points for Part A and Part B Respectively - Wound Area(cm ²)		SAC
3	PD	Exhibit N	Listing PD Endpoints by Treatment and Time Points for Part A and Part B Respectively - Wound Depth(mm)		SAC
4	PD	Exhibit N	Listing PD Endpoints by Treatment and Time Points for Part A and Part B Respectively - Wound Volume(mm ³)		SAC
5	PD		SAS output for mixed effects models Analysis of physical characteristics of wound healing		SAC, in stream
6	All Subjects	AE2	Listing of Relationship Between System Organ Class and Verbatim Text		SAC, in stream
7	PD	LB12	Listing of Exploratory Biomarker Parameters	List all data, flag if out of range	SAC

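### SAP 8.7 flags high hemoglobin only against 1.1 × ULN, so the protocol's 1.5 g/dL rise over own baseline usually goes unflagged and no titled display counts it by regimen

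*SAP*

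**What the plan says.** Protocol 1.4.1.1 names hemoglobin elevation as the systemic effect to be contained: "doses will be selected to minimize systemic exposure of the compound to limit elevations in hemoglobin". Protocol 4.5.1.1 gives the rule: "A patient that experiences an absolute increase in hemoglobin of 1.5g/dL above their baseline level at any time will be withdrawn from the study".

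SAP 8.7 defines values of potential clinical importance (PCI) separately for healthy volunteers and for patients. The hemoglobin rows are the same in both, in g/L:
- Low: "< -25 decrease from baseline", read here as a fall of more than 25 g/L.
- High: 1.1 × ULN for males and for females. Whether this means > or ≥ is not stated.

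The same section does use rise-from-baseline limits elsewhere: creatinine ("22 increase from baseline", in µmol/L) and ECG ("Increase from baseline QTc").

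The hematology displays titled in SAP 14.1 are a general summary (LB1), "Summary of Hematology Data Outside the Reference Range" (LB2), and listing no. 13 in 14.1.5, "Listing of all Clinical Hematology Laboratory Data for Subjects with Abnormalities of Potential Clinical Importance". The only safety table titled as a change from baseline is for ECG.

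**The concern.** Safety is a primary endpoint, and a rise in hemoglobin is the systemic effect that the dose rationale is built to limit. The SAP's high flag is tied to the population reference limit, whereas the protocol acts on change from the subject's own baseline. A subject can therefore meet the protocol's withdrawal value and get no flag. Because the only titled hematology listing is restricted to subjects with a PCI abnormality, a missing flag also keeps the subject out of that listing. The report could then be silent, by regimen, on the one hemoglobin change the protocol acts on, whether the answer is none or a few.

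**Working it through.** **Inputs.** Stopping value 1.5 g/dL = 15 g/L (Protocol 4.5.1.1). High PCI limit 1.1 × ULN (SAP 8.7). Laboratory baseline is Day 1 pre-dose (SAP 8.5). The documents give no ULN or reference range, so ULN 130 to 180 g/L and a range width W of 30 to 40 g/L are assumed. The plan states no figure on this point to reproduce.

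**Baseline from which a rise of exactly 15 g/L reaches the flag.** Baseline = 1.1 × ULN − 15; its distance from ULN = 0.1 × ULN − 15, which is zero at ULN 150.

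| Assumed ULN (g/L) | 1.1 × ULN | Baseline needed | Distance from ULN |
|---|---|---|---|
| 130 | 143 | 128 | −2 |
| 140 | 154 | 139 | −1 |
| 150 | 165 | 150 | 0 |
| 160 | 176 | 161 | +1 |
| 170 | 187 | 172 | +2 |
| 180 | 198 | 183 | +3 |

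Above ULN 150, no subject with an in-range baseline can be flagged at exactly +15 g/L. At 150, a subject starting at 150 is flagged under ≥ and not under >.

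**Share of the reference range from which the flag is reached.** max(0, 15 − 0.1 × ULN)/W:
- ULN 130: 2/40 to 2/30 = 5.0% to 6.7%.
- ULN 140: 1/40 to 1/30 = 2.5% to 3.3%.
- ULN 150: at most the single boundary value.
- Above 150: none.

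**Rise needed by a subject starting 15 g/L below ULN.** 0.1 × ULN + 15 = 28 g/L (ULN 130) to 33 g/L (ULN 180), which is 28/15 = 1.9 to 33/15 = 2.2 times the stopping value.

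**Share of subjects flagged.** Assume normally distributed baselines, SD = range width/3.92, and six assumed ranges with ULN 150 to 180 g/L.

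| Baseline mean | Flagged at +15 g/L | Flagged at +25 g/L |
|---|---|---|
| 15 g/L below mid-range | 0.03% or less | under 1% |
| Mid-range | 1.4% to 2.5% | 8% to 20% |
| 1 SD above mid-range | 11% to 17% | 35% to 56% |

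At the stopping value at least 83% are unflagged in every case tried. Larger rises are flagged more often.

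**Reference-range table.** A baseline at or below ULN − 15 plus 15 is at or below ULN, so that subject is not above range. With baselines centred mid-range, about 23% to 39% of subjects rising by 15 g/L would end above ULN; 1 SD higher, about 60% to 76%. Going by its title, this table also does not measure change from own baseline.

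**Who can start above ULN.** Protocol 5.2.1 excludes healthy volunteers above ULN. Protocol 5.3.2 sets no upper hemoglobin limit for DFU patients, so some may start above ULN and be flagged.

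**Scale.** One Part B cohort (SAP 3) with a target of 16 subjects (SAP 3.1) and three post-baseline safety-lab visits (Days 7 and 15 and the 7–10 day follow-up; Protocol 4.6.2) gives 16 × 3 = 48 values. Part A adds to this.

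**The case against.** The best case against is that the SAP deliberately keeps laboratory safety descriptive: SAP 10 leaves it to investigator review without formal analysis. Hemoglobin is also watched during conduct, because escalation decisions take it into account and unblinded sponsor staff review safety data before each escalation. A subject who meets the stopping rule must be withdrawn and so should appear in the disposition summary and the withdrawal listing, perhaps also in AE outputs. One who was not withdrawn should surface in the deviation review. SAP 8.1 promises that all data will be listed. The Exhibit L note foresees change-from-baseline summaries of laboratory parameters by treatment; if untransformed, their maximum would show whether any rise reached 15 g/L.

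Much of this stands, and it is why the point is minor. These routes are indirect, however:
- Day 15 and follow-up laboratory tests come after the last dose on Day 14, so a rise first seen then may leave no withdrawal record.
- A laboratory value becomes an AE only if the investigator judges it clinically significant (Protocol 12.1).
- No entry in SAP 14.1 cites Exhibit L, and no full hematology listing is titled there.
- The inner layout of the LB1, LB2 and withdrawal shells is not shown, so the claim is limited to display titles, and LB1 is not relied on either way.

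Hemoglobin is also named as an example of a circulating HIF biomarker (SAP 2.2.2). That route adds little. Listing no. 7 in 14.1.6 ("List all data, flag if out of range") would show the values but flag them only against a range, and Exhibit Z gives change as mean and SE. Protocol Table 5 places hemoglobin under hematology, so it may not enter those displays at all.

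**Conclusion.** The concern holds, as a minor one. The PCI rule usually misses a subject at the protocol's stopping value, and no display titled in SAP 14.1 directly identifies such subjects or counts them by regimen. The word *usually* rests on the assumed ULNs and baseline distributions, and it applies to rises at or near 15 g/L. The gap itself, a fall-from-baseline limit with no matching rise limit, is plain in SAP 8.7 and needs no assumption.

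The practical consequence is small. SAP 1 records Part A systemic exposure below quantification. The Amendment 7 rationale in Protocol Appendix 3 reports levels below 0.10 ng/mL with 1% ointment at 100 mg/cm². Rises of this size are therefore unlikely, the count would most likely document that none occurred, and with one Part B cohort a reader could check by hand if full data are listed.

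**What to change.** In SAP 8.7, for both populations, add a High criterion for hemoglobin: increase from baseline at or above the stopping value stated in Protocol 4.5.1.1 (currently 15 g/L), with baseline as in SAP 8.5. Apply it to the existing PCI hematology listing (14.1.5 no. 13). Add one table to 14.1.2 giving n (%) of subjects by regimen who meet it at any post-baseline visit. State whether the 1.1 × ULN rule is > or ≥. This changes reporting only and leaves the stopping rule as it is; Protocol 4.5.1.1 speaks of a patient, so the healthy-volunteer row is for reporting consistency.

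The cost is one criterion row per population and one table. Hemoglobin is already collected. The drawback is one more output in an SAP whose displays were cut back after the indication was terminated.
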